5. STUDY ENROLLMENT AND WITHDRAWAL

Only subjects who meet all of the inclusion and none of the exclusion criteria will be eligible for enrollment into this study. Exemptions may be granted on Inclusion/Exclusion Criteria pending Medical Lead Approval.

This study will enroll fifty healthy male and female subjects ages 18 to 55 years old in five cohorts.

Alternates who meet all eligibility criteria may effectively have their check-in at the same time as the lead two subjects and be rolled over into the next group within that cohort but will not be dosed until dosing for that cohort begins. Alternates not enrolled into the cohort are eligible for enrollment in subsequent cohorts but would have to undergo re-screening if more than 14 days have passed since their initial screening visit.

5.1. Subject Inclusion Criteria

All must be answered yes for the subject to be eligible for study participation

- 1. Informed consent understood and signed
- 2. Healthy male or healthy, non-pregnant, non-lactating female
- 3. Willingness to comply and be available for all protocol procedures for the duration of the study
- 4. Between 18 and 55 years of age on the day of dosing
- 5. Body Mass Index (BMI) of ≥ 18.5 and $\leq 35 \text{ kg/m}^2$
- 6. Female subjects of childbearing potential must have a negative serum pregnancy test at screening and negative urine test on Day 1 prior to dosing
 - Note: A woman is considered of childbearing potential unless post-menopausal (≥ 1 year without menses or without other known or suspected cause and appropriately elevated FSH) or surgically sterilized via bilateral oophorectomy or hysterectomy
- 7. Females of childbearing potential and males agree to use acceptable contraception for the duration of the study.
 - Note: These include progestin implants, intrauterine devices (IUDs), surgical (hysterectomy or tubal ligation; vasectomy) or abstinence. Use of methods such as progestin injectables, combined oral hormonal contraceptives, condoms, and diaphragms will not be acceptable when used alone, but they could be considered, if used in combination with another method (for example, a female using combined oral contraceptives if her male partner is sterile, or if she and her non-sterile male partner use a double-barrier method), after consultation with the RGS ML. All males will be required to use a barrier method (condoms) for the duration of the study
- 8. Screening laboratory tests are within normal ranges or outside the normal ranges and considered not clinically significant by the Principal Investigator
 - If urinalysis by dipstick is abnormal, a complete urinalysis with microscopic evaluation will be performed and the results will supersede the results of the dipstick for blood, glucose, and protein.
 - Menstruating females failing inclusion criteria due to positive blood on urine test may be retested following cessation of menses.
 - Other laboratory values that are outside the range of eligibility but are thought to be due to an acute condition or collection or laboratory error may be repeated once.
- 9. The urine drug screen is negative
- 10. Breathalyzer test or blood/saliva alcohol test is negative and subjects agrees to abstain from alcohol consumption for a period of 2 days prior to dosing and 2 days prior to any study visit
- 11. Agree to minimize risk of SARS-CoV-2 infection

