	 A blinded interim analysis planned for this study. A blinded interim analysis is planned to analyze all PK samples through Day 30 for all subjects in Cohorts 1 and 2.
	 A second blinded interim analysis is planned to analyze all PK samples after all subjects in Cohorts 1-3 complete Day 60. A third interim analysis is planned to analyze safety and PK after all subjects in cohort 5 complete Day 60.
	There is also an interim clinical study report (CSR) planned after subjects in Cohorts 1 through 4 complete Day 90.
Inclusion Criteria	 Informed consent understood and signed Healthy male or healthy, non-pregnant, non-lactating female Willingness to comply and be available for all protocol procedures for the duration of the study Between the ages of 18 and 55, inclusive on the day of dosing Body Mass Index (BMI) of ≥18.5 and ≤35 kg/m² Female subjects of childbearing potential must have a negative serum pregnancy test at screening and negative urine pregnancy test on Day 1 prior to dosing. Note: A woman is considered of childbearing potential unless post- menopausal (≥ 1 year without menses without other known or suspected cause and appropriately elevated FSH) or surgically sterilized via bilateral oophorectomy or hysterectomy Females of childbearing potential and males agree to use acceptable contraception for the duration of the study Note: These include progestin implants, intrauterine devices (IUDs), surgical (hysterectomy or tubal ligation; vasectomy) or abstinence. Use of methods such as progestin injectables, combined oral hormonal contraceptives, condoms, and diaphragms will not be acceptable when used alone, but they could be considered, if used in combination with another method (for example, a female using combined oral contraceptives if her male partner is sterile, or if she and her non-sterile male partner use a double-barrier method), after consultation with the RGS ML. All males will be required to use a barrier method (condoms) for the duration of the study Screening laboratory tests are within normal ranges or outside the normal ranges and considered not clinically significant by the Principal Investigator If urinalysis by dipstick is abnormal, a complete urinalysis with

1	
	microscopic evaluation will be performed and the results will supersede
	the results of the dipstick for blood, glucose, and protein.
	10. Menstruating females failing inclusion criteria due to a positive blood on
	urine test may be retested following cessation of menses.

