7.5.1.2. Drug Screen

A urine toxicology screen will be performed to detect for the presence of the following: cocaine (and metabolite), barbiturates, benzodiazepines, opiates, THC, methamphetamine/amphetamine, methadone and PCP. The results must be negative for eligibility into the study. A breathalyzer test or blood/saliva alcohol test will also be performed, and results must be negative for eligibility into the study.

7.5.1.3. **Pregnancy Testing**

For women of child-bearing potential, a serum pregnancy test will be done at screening and must be negative. A urine pregnancy test will be done at Visit 2 (Day 1), which must be reported as negative before dosing. A urine pregnancy test will be repeated on Day 4, Day 45, Day 120, 150, Day 180, and 365.

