7.5.1.4. Screening Laboratory Tests

The following laboratory tests will be performed at screening:

• Hematology: hemoglobin, WBC with differential, absolute neutrophil count and platelet count. MCV, MCH, MCHC, RDW, MPV, which are included in a complete blood count with differential, will not be graded.

- Chemistry: serum creatinine, BUN, calcium, total bilirubin, direct bilirubin, indirect bilirubin, alkaline phosphatase, PT, PTT, INR, ALT, AST, sodium, potassium, and total CK.
- Urinalysis: dipstick: Urine protein, blood and glucose must be negative or trace. Menstruating females failing with a positive blood on urine dipstick may be retested following cessation of menses. If dipstick is abnormal, a complete urinalysis with microscopic will be performed. When a urine dipstick is more than trace positive for blood (whether a menstruating female or other subject), that subject would not be excluded if the urine microscopic exam shows <5 RBC/HPF.
- FSH to confirm post-menopausal status for women ≥ 1 year without menses

Laboratory values that are outside the range of eligibility but are thought to be due to an acute condition or due to laboratory error may be repeated once. Laboratory values will be entered in the Clinical Labs Ecrf.

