8.1. Visit 1: Screening (Day -14 to Day -2)

After providing written informed consent, each subject will be assigned a Subject ID number (840-XXX-XXX) and undergo an eligibility assessment. The following will be done during the screening period (within 14 days prior to administration of study product). Results of screening tests and procedures will be evaluated by the investigator to determine eligibility prior to enrollment and randomization. The following procedures will be performed.

- Record demographics including age, gender, race and ethnicity. Obtain contact information.
- Obtain medical history. The medical history will include the following:
 - current medical diagnoses
 - past medical diagnoses
 - hospitalizations
 - major surgical procedures
 - blood transfusions or immunoglobulin within the last 6 months
 - live vaccines within the last 28 days
 - killed vaccines within the last 28 days
 - blood or plasma donation within the last 56 days
 - allergic reactions
 - drug and/or alcohol use disorder or dependence
 - receipt of investigational drug within the last 28 days
 - Receipt of monoclonal antibody in the past
- Documentation that the subject has not received an FDA approved vaccine for COVID-19 (Subjects may receive an approved COVID-19 vaccine after completing their Day 90 visit). For Cohort 5, subjects who received a COVID-19 vaccine within 14 days prior to enrollment are excluded.
- Review concomitant medication history, including all medications taken within the last 28 days
- Review current use of contraceptive methods and recent menstrual history (female subjects only)

- Perform abbreviated PE by licensed clinician listed on the Form FDA 1572 [examples include Medical Doctor, Nurse Practitioner and Physician's Assistant]
- Obtain height and weight and calculate BMI
- Take vital signs (systolic and diastolic blood pressure, pulse rate, respiratory rate, and oral temperature)
- Obtain fasting blood samples for viral serology, clinical laboratory screening tests including SARS-CoV-2 antibodies and RT-PCR for SARS-Co-V-2
- Obtain blood sample for serum pregnancy test for women of childbearing potential
- Obtain urine sample for dipstick urinalysis and urine toxicology
- Obtain 12-lead ECG
- Perform Breathalyzer test or blood/saliva alcohol test for recent alcohol use
- Counsel both men and women of childbearing potential on the avoidance of pregnancy

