APPENDIX A: SCHEDULE OF EVENTS

Protocol: ADM03820-001

Version 6.0 July 14, 2022

Study Visit	Screening ¹ 01	Baseline/Dosing 02	Discharge 03	04	05	06	07	08	09	10	11	12	13	14	Final Outpatient Visit / ET 15	TC ¹⁹ 16	TC¹⁹ 17
Study Day (Window)	-14 to -2	1	2	3	4	8±2	15±2	30±2	45±3	60±3	90±3	120±5	150±5	180±5	365±5	450± 5	540±5
SARS-CoV-2 Antibodies ¹⁸	Х																
RT-PCR ¹⁷	Х	Х															
Concomitant Medications ²	Х	Х	Х	Х	Х	Х	Х	Х	Х	Х	X	Х	Х	Х	Х	Х	Х
Randomization		Х															
Study Drug Administration		Х															
Future Use Sample ¹²		Х	Х			Х		Х									
Counsel on the avoidance of pregnancy	Х	Х	Х	Х	Х	Х	Х	Х	Х	Х	Х	Х	Х	Х	Х	Х	
AE Review		Х	Х	Х	Х	Х	Х	Х	Х	Х	Х	Х	Х	Х	Х	Х	Х
SAE Review		Х	Х	Х	Х	Х	Х	Х	Х	Х	Х	Х	Х	Х	Х	Х	Х

1. Screening will be completed within 14 days prior to administration of study drug and may require more than one visit.

2. Concomitant medications including all of the following: prescription drugs, over-the-counter drugs, herbs, vitamins, nutritional supplements, illicit and recreational substance use, birth control

3. PE includes height and weight at screening.

4. Vital Signs to include sitting diastolic and systolic blood pressure, heart rate, respiratory rate, and oral temperature. See section 8 for a schedule of when vital signs are to be obtained.

5. Screening Laboratory Tests that will include hemoglobin, WBC with differential, absolute neutrophil count and platelet count. MCV, MCH, MCHC, RDW, MPV, which are included in a complete blood count with differential, will not be graded, serum creatinine, BUN, calcium, total bilirubin, direct bilirubin, indirect bilirubin, alkaline phosphatase, PT, PTT, INR, ALT, AST, sodium, potassium, and total CK. Include FSH at screening to confirm post-menopausal status for women ≥ 1 year without menses

6. Clinical Safety Laboratory Tests that will include hemoglobin, WBC with differential, absolute neutrophil count and platelet count. MCV, MCH, MCHC, RDW, MPV, which are included in a complete blood count with differential, will not be graded, serum creatinine, BUN, calcium, total bilirubin, direct bilirubin, indirect bilirubin, alkaline phosphatase, PT, PTT, INR, ALT, AST, sodium, potassium, and total CK.

7. A serum pregnancy test will be obtained for all women of reproductive capacity. Results must be confirmed as negative before study product is dosed.

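### An extra *or* in Protocol section 5.1, criterion 6, makes the post-menopausal definition conflict with the Protocol Summary and with the FSH confirmation ordered elsewhere

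*Protocol*

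**What the plan says.** Criterion 6 in Protocol section 5.1 treats every woman as being of childbearing potential unless she is surgically sterilised (bilateral oophorectomy or hysterectomy) or post-menopausal. It describes post-menopausal as at least one "year without menses or without other known or suspected cause and appropriately elevated FSH". This is the operative eligibility list, which opens with "All must be answered yes for the subject to be eligible for study participation".

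The Protocol Summary, under inclusion criterion 6, gives the definition as at least one "year without menses without other known or suspected cause and appropriately elevated FSH".

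Three other places give the purpose of the FSH test. Section 7.5.1.4 lists "FSH to confirm post-menopausal status for women ≥ 1 year without menses". Appendix A, note 5, says "Include FSH at screening to confirm post-menopausal status for women ≥ 1 year without menses", and note 5 to the schedule of events in the SAP repeats it.

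The classification then feeds other requirements. Criterion 7 in section 5.1 states "Females of childbearing potential and males agree to use acceptable contraception for the duration of the study". Section 8.1 asks sites to "Obtain blood sample for serum pregnancy test for women of childbearing potential". Section 7.5.1.3, in a paragraph that opens by limiting itself to women of childbearing potential, adds "A urine pregnancy test will be repeated on Day 4, Day 45, Day 120, 150, Day 180, and 365".

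**The concern.** Two current parts of the same protocol define one eligibility term differently, and the part sites must answer item by item has the looser wording. The definition decides which women must use contraception and which are tested for pregnancy after a single dose. Section 4 describes the study as first-in-human, and section 2.1.3 says the antibodies carry a mutation meant to extend their half-life. A woman wrongly classed as post-menopausal could therefore go through follow-up without those protections.

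The amendment history does not explain the difference. The summary of changes for version 3.0 records that the FSH test was added to the screening laboratory list. No entry records a change to the definition.

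**Working it through.** No arithmetic applies, so the check sets the texts side by side.

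**Step 1: the conditions.** Let A be at least one year without menses, B be no other known or suspected cause for it, and C be appropriately elevated FSH.

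- Protocol Summary: A and B and C.
- Section 5.1, usual reading (*and* binds before *or*): A or (B and C).
- Section 5.1, other grouping: (A or B) and C.

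**Step 2: where the three rules part.** The profiles below are logical cases, not frequencies.

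| Profile | Summary | 5.1, usual reading | 5.1, other grouping |
|---|---|---|---|
| A, B and C all hold | post-menopausal | post-menopausal | post-menopausal |
| A and C hold, but another cause is known | no | post-menopausal | post-menopausal |
| A and B hold, FSH not elevated | no | post-menopausal | no |
| A holds, another cause is known, FSH not elevated | no | post-menopausal | no |
| B and C hold, less than one year without menses | no | post-menopausal | post-menopausal |

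In the three remaining profiles (A fails, and B or C or both fail) all three rules say no. Each grouping of 5.1 therefore admits profiles that the Summary rejects. Two are admitted under both groupings: elevated FSH with a known other cause, and elevated FSH before a full year has passed.

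**Step 3: which text reflects the intent.** Section 7.5.1.4 and the two schedule notes order FSH as confirmation in women who already have a year without menses. If A alone were enough, there would be nothing to confirm. These texts agree with the Summary.

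**Step 4: what depends on the classification.**

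- Contraception for women, through criterion 7.
- The screening serum test, through criterion 6 and sections 7.5.1.3 and 8.1. Appendix A, note 7, uses a different and undefined term, reproductive capacity.
- The follow-up urine tests on Days 4, 45, 120, 150, 180 and 365. Sections 8.5, 8.9 and 8.12 to 8.15 word them for women of childbearing potential.

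**Step 5: the Day 1 urine test.** Criterion 6 and section 7.5.1.3 tie it to childbearing potential, while section 8.2 words it for women generally. The urine-test row in Appendix A names no population at all. The texts do not settle which tests a misclassified woman would miss, so no count is given here.

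**The case against.** The strongest reply is that this is a slip of one word and the rest of the protocol already resolves it. Much of that stands. The Summary is clean, and three separate notes order FSH to confirm the status. A site that uses FSH as section 7.5.1.4 directs would not accept a woman with a year without menses and a non-elevated FSH. What then remains is mainly a woman with elevated FSH and another known cause.

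Other safeguards narrow the risk further. Hysterectomy and bilateral oophorectomy are exempted separately in the same note. Users of progestin implants or intrauterine devices already satisfy criterion 7. Contraception and menstrual history are reviewed at Visit 1, section 8.2 words the Day 1 urine test for women generally, and exclusion criterion 10 in section 5.2 bars pregnant women.

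The reply does not remove the point entirely. Section 7.5.1.4 orders the test but does not say which result changes a woman's classification. Only the note to criterion 6 does that, and in section 5.1 that note is the faulty text.

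It can also be argued that a correction would come too late. Apart from a company name change, version 7.0 (August 2023) only shortens follow-up for cohort 5, the last cohort, and the SAP finalised in September 2023 is written for the final analysis. This suggests that dosing was finished or nearly so, but the documents do not state enrolment status.

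**Conclusion.** The inconsistency is real, sits in current eligibility text, and is minor. Section 5.1 does not state the rule given in the Summary under either grouping, and the rule governs contraception and pregnancy testing. The practical risk is small because the intent is recoverable and FSH is drawn in any case. No endpoint, sample size or analysis is affected.

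Three stronger conclusions might be inferred, and the documents support none of them.

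- That the protocol exempts any woman with a year without menses, whatever the cause or her FSH. This is only the literal reading of one sentence, and the FSH confirmation in section 7.5.1.4, Appendix A and the SAP contradicts it.
- That a fixed number of pregnancy tests would be missed. The protocol's own texts disagree about the Day 1 urine test, and a bare row label in Appendix A cannot be treated as a competing rule.
- That women were in fact misclassified. The documents give no information on this, and the number at risk cannot be derived from them.

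The verdict rests on one assumption: that the Summary states the intended definition. The FSH notes support it.

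**What to change.** Delete the first *or* from the note to criterion 6 in section 5.1, so that it matches the Summary: at least one "year without menses without other known or suspected cause and appropriately elevated FSH". Elevated FSH then becomes a required condition in the operative list. The change sets no numeric FSH threshold; what counts as appropriately elevated is left as it stands.

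The cost is one word in an amendment, with the IRB approval that section 14.2 requires. No procedure is added, because FSH is already drawn at screening. If dosing is complete, the change serves only to let sites recheck the classification of women still in follow-up and to correct the record.

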5.2. Subject Exclusion Criteria

Subjects meeting any of the following exclusion criteria are not eligible for participation.

All must be answered no for the subject to be eligible for study participation

- 1. History of a chronic medical condition that would either interfere with the accurate assessment of the objectives of the study or increase the risk profile of the subject.
- 2. Subjects with cardiovascular disease
- 3. Subjects with diabetes
- 4. Subjects with pulmonary diseases such as COPD or asthma
- 5. History of severe allergic reaction of any type to medications, bee stings, food, or environmental factors or hypersensitivity or reaction to immunoglobulins.
- 6. A marked baseline prolongation of QT/QTc interval (e.g., repeated demonstration of a QTc interval >450 milliseconds)
- 7. Clinically significant abnormal electrocardiogram at screening.
 - Note: Clinically significant abnormal ECG results include but not limited to: complete left or right bundle branch block; other ventricular conduction block; 2nd degree or 3rd degree atrioventricular (AV) block; sustained ventricular arrhythmia; sustained atrial arrhythmia; two Premature Ventricular Contractions in a row; pattern of ST elevation felt consistent with cardiac ischemia; or any condition deemed clinically significant by a study investigator
 - Incomplete right bundle branch block is not exclusionary if there are no abnormal ECG findings and there is no clinical history or evidence on physical examination to indicate cardiac disease.
- 8. Positive serology results for HIV, HbsAg, or HCV antibodies
- 9. Febrile illness with temperature \geq 38°C within 7 days of dosing
- 10. Female subject is pregnant or breastfeeding
- 11. Donated blood or plasma within 56 days of enrollment
- 12. Known allergic reactions to any of the study product components present in the formulation or in the processing, as listed in the Investigator Brochure
- 13. Treatment with another investigational drug within 28 days of dosing
- 14. Treatment with a monoclonal antibody within 3 months of enrollment.
- 15. Positive serology results for SARS-CoV-2 antibodies (Not applicable for Cohort 5).
- 16. Positive results from a reverse transcriptase polymerase chain reaction (RT-PCR) test for SARS-Co-V-2

- 17. Receipt of antibody (e.g. TIG, VZIG, IVIG, IM gamma globulin) or blood transfusion within 6 months or within 5 half-lives of the specific product given
- 18. Active drug or alcohol use disorder or dependence that, in the opinion of the investigator, would interfere with adherence to study requirements
- 19. Use of H1 antihistamines or beta-blockers within 5 days of dosing
- 20. Use of any prohibited medication within 28 days prior to screening or planned use during the study period
 - Note: Prohibited medications include immunosuppressives (except Nonsteroidal Anti-Inflammatory Drugs [NSAIDS]); immune modulators; oral corticosteroids (topical/intranasal steroids are acceptable); anti-neoplastic agents
- 21. Any specific condition that in the judgment of the investigator precludes participation because it could affect subject safety
- 22. Plans to enroll or is already enrolled in another clinical trial* that could interfere with safety assessment of the investigational product at any time during the study period
 - Note: Includes trials that have a study intervention such as a drug, biologic, or device
- 23. Is a study site employee or staff
 - Note: Site employees or staff include the Pis and sub-investigators or staff who are supervised by the PI or Sub-Investigators
- 24. Received an approved COVID-19 vaccine (subjects can receive an approved COVID-19 vaccine after completing their Day 90 visit. For Cohort 5, subjects who received a COVID-19 vaccine within 14 days prior to enrollment are excluded.

